7.4 Subgroup Analyses

Subgroup analyses will be performed for the primary efficacy variable by UNVA at baseline $(UNVA \le 20/80 \text{ or} > 20/80)$, iris color (brown or not brown), gender, race, and ethnicity.

7.5 Sample Size Calculation

The study consists of 4 parallel groups and 5 sequences of 2-day dosing periods within each group (see Figure 1). Each dosing period is separated by a washout of 14 ± 7 days and each sequence is tested 8 times resulting in 40 patients per group.

The sample size is deemed appropriate to build a response surface model that assesses the efficacy profile of the combination relative to monotherapies.

7.6 Interim Analyses

There will be no interim analyses.

8. Study Visit Schedule and Procedures

Please see Table 2 for a schematic of the schedule of visits and procedures and Figure 1 for a flowchart of the study visits.

8.1 Patient Entry Procedures

8.1.1 Overview of Entry Procedures

Prospective patients as defined by the criteria in Sections 4.3 and 4.4 (inclusion/exclusion criteria) will be considered for entry into this study.

8.1.2 Informed Consent and Patient Privacy

The study will be discussed with the patient and a patient wishing to participate must give informed consent prior to any study-related procedures or change in treatment. The patient must also give authorization and other written documentation in accordance with the relevant country and local privacy requirements (where applicable) prior to any study-related procedures or change in treatment.

Each patient that provides informed consent and/or assent will be assigned a patient number that will be used on patient documentation throughout the study.

8.2 Washout Intervals

Each dosing period will be separated by a washout of 14 ± 7 days.

8.3 Procedures for Final Study Entry

The results from screening ocular examinations must be evaluated and determined to be acceptable to the investigator prior to the patient's entry into the study. Furthermore, all female patients of childbearing potential MUST have a negative urine pregnancy test at screening and baseline (day 1) prior to randomization and initiation of study treatment. Each patient's ocular examination findings at screening and baseline (day 1) will be evaluated with respect to the entry criteria specified in Sections 4.3 and 4.4 for final determination of eligibility before the patient is randomized.

[figure not shown]
Patients will be considered to have enrolled in the study when they are randomized.

[figure not shown]
See Section 5.5 for the method for assignment to treatment groups/randomization.

[figure not shown]
8.4 Visits and Associated Procedures

[figure not shown]
Evaluations should be performed by the same evaluator throughout the study whenever possible. If it is not possible to use the same evaluator to follow the patient, then evaluations should overlap (examine the patient together and discuss findings) for at least 1 visit.

The following section provides a list of procedures for each scheduled visit. All ophthalmic procedures should be performed for each eye, unless otherwise noted. Additional information on the examination procedures, equipment, and techniques for the measures listed in this section is presented in Section 6.3.

8.5 Instructions for the Patients

After patients have signed the informed consent, they will be instructed as follows:

- Patients will be instructed to complete the study-related procedures as explained to them by the study site personnel.
- Patients will be instructed to refrain from swimming, being exposed to smoke, or other exposure that might cause eye irritation during the study
- If spectacles are worn for vision correction, patients should remember to bring the spectacles each time they visit the doctor's office.
- Patients must not read, use the computer, or look at cell phones/tablets without the use of reading glasses during any portion of the study visits. Note: Patients will be required to refrain from using their glasses during the near-vision tasks and associated near-vision task questionnaires, but *may* use their glasses to fill out other study related questionnaires.
- Patients will be instructed to strictly follow the study visit schedule and to report all changes in condition to the site.

- Patients will be instructed to maintain a stable dose of any concomitant medication used chronically.
- Patients will be instructed to report any changes to their medication at their next study visit, or to report any new medication(s) initiated during the study. Patients will also be reminded to contact the study site if they are experiencing any difficulties during their study participation.
- Patients will be reminded of the systemic and ocular medications/treatments that are prohibited for the duration of the study (see Section 4.5.2).

8.6 Unscheduled Visits

Additional examinations may be performed as necessary to ensure the safety and well-being of the patients during the study period. Unscheduled visit eCRFs should be completed for each unscheduled visit. For all parameters not measured, indicate "not done".

8.7 Compliance with Protocol

Patients will be scheduled for follow-up visits, and these should occur as close as possible to the day specified in the visit schedule.

At each postbaseline visit, the investigator or designee will ask patients if they have used any concomitant medications or had any procedures performed since the previous visit.

All doses of study medication will be administered by study personnel, therefore patient compliance with the study medication regime will not be monitored.

8.8 Early Discontinuation of Patients

Patients may voluntarily withdraw from the study at any time.

Notification of early patient discontinuation from the study and the reason for discontinuation will be made to the sponsor and will be clearly documented on the appropriate case report form.

8.9 Withdrawal Criteria

A patient may be withdrawn from the study if it is deemed by the investigator or Allergan that it is unsafe for the patient to continue in the study. Patients who are withdrawn from the study will not be replaced.

If the patient withdraws prior to completing the study, the procedures outlined for the visit 2/study exit should be performed at the last visit attended (see Section 8.4.3).

If a female patient becomes pregnant during the study, the investigator will notify Allergan immediately after the pregnancy is confirmed and the patient will be exited from the study (see Section 9.5).

8.10 Study Termination

The study may be stopped at his/her study site at any time by the site investigator. Allergan may stop the study (and/or the study site) for any reason with appropriate notification.

9. Adverse Events

Adverse events occurring during the study will be recorded on an adverse event case report form. If adverse events occur, the first concern will be the safety of the study participants.

9.1 Definitions

9.1.1 Adverse Event

An adverse event is any untoward medical occurrence in a patient or clinical investigation patient administered a pharmaceutical product and that does not necessarily have a causal relationship with this treatment. An adverse event can therefore be any unfavorable and unintended sign (including an abnormal laboratory finding), symptom, or disease temporally associated with the use of a medicinal (investigational) product, whether or not related to the medicinal (investigational) product. In addition, during the screening period, adverse events will be assessed regardless of the administration of a pharmaceutical product.

Note: Adverse events must be collected once informed consent has been obtained, regardless of whether or not the patient has been administered study drug.

Progression of treatment indication including new or worsening of anticipated clinical signs or symptoms, which are collected as clinical efficacy variables and assessed as unequivocally associated with the disease progression and /or lack of efficacy, should NOT be reported as adverse events unless the disease progression is greater than anticipated in the natural course of the disease.

Adverse events will be assessed, documented, and recorded in the electronic case report form (eCRF) throughout the study (ie, after informed consent has been obtained). At each visit, the investigator will begin by querying for adverse events by asking each patient a general,

non-directed question such as "How have you been feeling since the last visit?" Directed questioning and examination will then be done as appropriate. All reported adverse events will be documented on the appropriate case report form.

9.1.2 Serious Adverse Event

A serious adverse event is any adverse event occurring at any dose that results in any of the following outcomes: death, a life-threatening adverse event, inpatient hospitalization or prolongation of existing hospitalization, a persistent or significant disability/incapacity, or a congenital anomaly/birth defect. Important medical events that may not result in death, be life-threatening, or require hospitalization may be considered a serious adverse event when, based upon appropriate medical judgment, they may jeopardize the patient or patient and may require medical or surgical intervention to prevent one of the outcomes listed in this definition. (See Section 9.3 for procedures for reporting a serious adverse event.)

Allergan considers all cancer adverse events as serious adverse events. In addition, Allergan considers any abortion (spontaneous or nonspontaneous) as a serious adverse event.

Preplanned surgeries or procedures for pre-existing, known medical conditions for which a patient requires hospitalization is not reportable as a serious adverse event.

Any preplanned surgery or procedure should be clearly documented in the site source documents by the medically qualified investigator at the time of the patient's entry into the study. If it has not been documented at the time of the patient's entry into the study, then it should be documented as a serious adverse event and reported to Allergan.

9.1.3 Severity

A clinical determination will be made of the intensity of an adverse event. The severity assessment for a clinical adverse event must be completed using the following definitions as guidelines:

Mild Awareness of sign or symptom, but easily tolerated.

Moderate Discomfort enough to cause interference with usual activity.

Severe Incapacitating with inability to work or do usual activity.

9.1.4 Relationship to Study Drug or Study Procedure

A determination will be made of the relationship (if any) between an adverse event and the study drug or study procedure, as applicable. A causal relationship is present if a determination is made that there is a reasonable possibility that the adverse event may have been caused by the drug or study procedure.

9.2 Procedures for Reporting Adverse Events

Any adverse event must be recorded on the appropriate case report form.

All adverse events that are drug-related and unexpected (not listed as treatment-related in the current Investigator's Brochure) must be reported to the governing Institutional Review Board/Independent Ethics Committee (IRB/IEC) as required by the IRB/IEC, local regulations, and the governing health authorities. Any adverse event that is marked 'ongoing' at the exit visit must be followed-up as appropriate.

9.3 Procedures for Reporting a Serious Adverse Event

Any serious adverse event occurring during the study period (beginning with informed consent) and for at least 28 days after the last dose of study drug must be immediately reported but no later than 24 hours after learning of a serious adverse event. Serious adverse events must be reported to Allergan (or Agent of Allergan as listed on the Allergan Study Contacts Page and recorded on the serious adverse event form. All patients with a serious adverse event must be followed up and the outcomes reported. The investigator must supply the sponsor and the IRB/IEC with any additional requested information (eg, autopsy reports and discharge summaries).

In the event of a serious adverse event, the investigator must:

- 1. Notify Allergan immediately by fax or email using the serious adverse event form (contact details can be found on page 1 of the serious adverse event form); phone numbers and relevant Allergan personnel contacts are also on the front page of protocol and Study Contacts Page.
- 2. Obtain and maintain in his/her files all pertinent medical records, information, and medical judgments from colleagues who assisted in the treatment and follow-up of the patient.
- 3. Provide Allergan with a complete, written description of the adverse event(s) on the serious adverse event form describing the event chronologically, including any

treatment given (eg, medications administered, procedures performed) for the adverse event(s). Summarize relevant clinical information about the event: signs, symptoms, diagnosis, clinical course and relevant clinical laboratory tests, etc. Include any additional or alternative explanation(s) for the causality which includes a statement as to whether the event was or was not related to the use of the investigational drug.

4. Promptly inform the governing IRB/IEC of the serious adverse event as required by the IRB/IEC, local regulations, and the governing health authorities.

9.4 Procedures for Unmasking of Study Medication

When necessary for the safety and proper treatment of the patient, the investigator can unmask the patient's treatment assignment to determine which treatment has been assigned and institute appropriate follow-up care. When possible, the sponsor (Allergan Medical Safety Physician) should be notified prior to unmasking study medication. The investigator should inform the sponsor (Allergan Medical Safety Physician) of the unmasking if there is no notification prior to the unmasking.

The treatment assignment for the patient can be determined by designated site personnel logging into the IxRS via password protected access. The reason for breaking the code must be recorded in the patient's source documents.

9.5 Procedures for Pregnancy Follow-up and Reporting (If Applicable)

If a female becomes pregnant during the study, the investigator will notify Allergan immediately after the pregnancy is confirmed, and the patient will be exited from the study after appropriate safety follow-up. The investigator will (1) notify the patient's physician that the patient was enrolled in this study and treated with an investigational drug ocular oxymetazoline, ocular pilocarpine, or the combination of oxymetazoline and pilocarpine, and (2) follow the progress of the pregnancy. The investigator must document the outcome of the pregnancy and provide a copy of the documentation to Allergan.

It is not known if the investigational products may have teratogenic or mutagenic effects, as studies to evaluate these effects in humans have not been done. There are no adequate and well-controlled studies of pilocarpine or oxymetazoline administration in pregnant women. In addition, it is not known if these products are excreted in human milk.

10. Administrative Items

This protocol is to be conducted in accordance with the applicable Good Clinical Practice (GCP) regulations and guidelines, eg, the International Conference on Harmonisation (ICH) Guideline on GCP.

10.1 Protection of Human Patients

10.1.1 Compliance with Informed Consent Regulations (US 21 CFR Part 50) and Relevant Country Regulations

Written informed consent is to be obtained from each patient prior to any study-related activities or procedures in the study, and/or from the patient's legally authorized representative. If the patient is under the legal age of consent, the consent form must be signed by the legally authorized representative in accordance with the relevant country and local regulatory requirements.

10.1.2 Compliance With IRB or IEC Regulations

This study is to be conducted in accordance with IRB regulations (US 21 CFR Part 56.103) or applicable IEC regulations. The investigator must obtain approval from a properly constituted IRB/IEC prior to initiating the study and re-approval or review at least annually. Allergan is to be notified immediately if the responsible IRB/IEC has been disqualified or if proceedings leading to disqualification have begun. Copies of all IRB/IEC correspondence with the investigator should be provided to Allergan.

10.1.3 Compliance With Good Clinical Practice

This protocol is to be conducted in accordance with the applicable GCP regulations and guidelines.

10.1.4 Compliance With Electronic Records; Electronic Signatures Regulations (US 21CFR Part 11)

This study is to be conducted in compliance with the regulations on electronic records and electronic signature.

10.2 Changes to the Protocol

The investigator must not implement any deviation from or changes of the protocol without approval by Allergan and prior review and documented approval/favorable opinion from the IRB/IEC of a protocol amendment, except where necessary to eliminate immediate hazards

58

to study patients, or when the changes involve only logistical or administrative aspects of the study (eg, change in monitors, change of telephone numbers).

10.3 Patient Confidentiality

A report of the results of this study may be published or sent to the appropriate health authorities in any country in which the study drug may ultimately be marketed, but the patient's name will not be disclosed in these documents. The patient's name may be disclosed to the Sponsor of the study, Allergan, or the governing health authorities or the FDA if they inspect the study records. Appropriate precautions will be taken to maintain confidentiality of medical records and personal information.

10.3.1 Patient Privacy

Written authorization (US sites only), data protection consent (European sites only), and other documentation in accordance with the relevant country and local privacy requirements (where applicable) is to be obtained from each patient prior to enrollment into the study, and/or from the patient's legally authorized representative in accordance with the applicable privacy requirements (eg, the Health Insurance Portability and Accountability Act Standards for Privacy of Individually Identifiable Health Information ("HIPAA"), European Union Data Protection Directive 95/46/EC ["EU Directive"]).

In accordance with HIPAA requirements, additional purposes of this study may include publishing of anonymous patient data from the study.

10.4 Documentation

10.4.1 Source Documents

Source documents may include a patient's medical records, hospital charts, clinic charts, the investigator's patient study files, as well as the results of diagnostic tests such as X-rays, laboratory tests, and electrocardiograms. The investigator's copy of the case report forms serves as part of the investigator's record of a patient's study-related data.

The following information should be entered into the patient's medical record:

- Patient's name.
- Patient's contact information.

- The date that the patient entered the study, patient number, and patient randomization [or medication kit] number.
- The study title and/or the protocol number of the study and the name of Allergan.
- A statement that informed consent was obtained (including the date). A statement that written authorization (US sites only), data protection consent (EU sites only), or other country and local patient privacy required documentation for this study has been obtained (including the date).
- Dates of all patient visits, time of day, and protocol designated hours for all patient visits/timepoints.
- All concurrent medications (List all prescription and non-prescription medications being taken at the time of enrollment. At each subsequent visit, changes to the list of medications should be recorded.)
- Occurrence and status of any adverse events.
- The date the patient exited the study, and a notation as to whether the patient completed the study or reason for discontinuation.
- The results of laboratory tests performed by the site (ie, results of urine pregnancy tests).
- Patient medical, surgical, and ophthalmic histories (including demographics);
 screening ophthalmological assessments; and for females, documentation of non-childbearing potential or results of pregnancy test.
- Key study variables

Source documentation practices must follow Section 4.0 of ICH E6, Good Clinical Practice: Consolidated Guidance and ALCOA (ie, records must be Attributable, Legible, Contemporaneous, Original, and Accurate).

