Safety measures will be analyzed using the safety population. Medical Dictionary for Regulatory Activities (MedDRA) nomenclature will be used to code adverse events. Incidence rates of each treatment-emergent adverse event will be summarized by primary system organ class and preferred term. Treatment-emergent adverse events are events that occur or worsen after the treatment. Summary tables will be generated for all treatment-emergent adverse events regardless of causality as well as for those considered to be treatment-related. The adverse events will be classified into ocular and nonocular types and will be summarized separately as described below. Ocular adverse events and other ocular evaluations will be summarized using eye as the experimental unit by dosing group and dosing period. Nonocular adverse events and other nonocular assessments (eg, vital signs) will be summarized using patient as the experimental unit by dosing group and dosing period.

Detailed descriptions of the safety analyses for adverse events and other safety measures will be documented in analysis plan.

Sample Size Calculation:

The study consists of 4 parallel groups and 5 sequences of 2-day dosing periods within each group (see Figure 1). Each dosing period is separated by a washout of 14 ± 7 days and each sequence is tested 8 times resulting in 40 patients per group.

The sample size is deemed appropriate to build a response surface model that assesses the efficacy profile of the combination relative to monotherapies.

1. Background and Clinical Rationale

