**Table 5-23 AE Terms**

Term	Description
Treatment-emergent	An event that initially occurs or increases in intensity on or after the treatment start date, where: 

• Treatment start date <math>\leq</math> event start date <math>\leq</math> following washout period before the next 2-day dosing period or last dose date + 30 days

On-therapy	An event where: 

• Treatment start date <math>\leq</math> event start date <math>\leq</math> following washout period before the next 2-day dosing period or last dose date + 30 days

[figure not shown]
AEs, encompassing abnormalities and surgeries reported as occurring after the Screening Visit, will be coded using MedDRA version 19.0 or newer. Unique subjects reporting AEs in the

following AE categories will be summarized by treatment group and overall for the Safety Population as follows:

[figure not shown]

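### SAP Table 5-23 assigns adverse events by calendar date, so one that starts or worsens on a period's first day before the first drop is charged to a treatment not yet given

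*Protocol*

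**What the plan says.** **Assignment rule (SAP 5.1.1.4.2, Table 5-23).** A treatment-emergent AE is "An event that initially occurs or increases in intensity on or after the treatment start date". The start date must be no earlier than the treatment start date and no later than the "following washout period before the next 2-day dosing period or last dose date + 30 days". The on-therapy definition uses the same date limits. SAP Table 6-1 makes the whole treatment start date Day 1, and SAP 6.4 imputes dates only to year, month and day.

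**Protocol definition (Protocol Summary, Safety).** "Treatment-emergent adverse events are events that occur or worsen after the treatment". SAP 5.2.2, which lists changes to the planned analyses, does not mention a change to this definition.

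**Timing (Protocol 5.6, 8.3, 9.1.1).** Drops are given at 8 AM, plus or minus one hour, on two consecutive days per period. At each visit "the investigator will begin by querying for adverse events". In period 1, ocular findings on day 1 are reviewed before randomization.

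**Recording (Protocol 9.2, 10.4.1).** "Any adverse event must be recorded on the appropriate case report form". The fields of that form are not shown. Separately, the medical record is to hold "Dates of all patient visits, time of day, and protocol designated hours for all patient visits/timepoints" and, for AEs, "Occurrence and status of any adverse events".

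**Use (SAP 5.1.1.1.6).** AEs are summarized by dosing group and dosing period.

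**The concern.** In a parallel-group trial with one treatment per patient, a date rule that includes the whole first day can only add a few pre-exposure events to the arm the patient is in anyway. Here each patient receives five treatments in turn. The same rule takes an event that arose while the previous treatment was the last one given and counts it under the next. It does so on a morning when the site is asking about AEs before dosing.

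AE rates by treatment are the evidence for the second clinical hypothesis, that a combination's safety and tolerability are no worse than the cumulative monotherapy findings. The protocol and SAP should therefore not classify the same event differently, and the rule in force should not charge a drug with an event that preceded it.

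**Working it through.** No stated figure depends on this point, so the check sets the two rules side by side and then sizes the exposed interval.

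**1. One event, two rules.** I read the treatment start date in Table 5-23 as the start of each dosing period, because the window's end is defined by the washout that follows.

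| AE onset or worsening | Protocol wording | SAP Table 5-23 |
|---|---|---|
| Day 1 of period 1, before the first drop | Not treatment-emergent | Treatment-emergent |
| Day 1 of periods 2 to 5, before the first drop | Not after the new treatment | Counted under the new treatment, outside the previous window |
| Earlier date, not worsened since | Previous treatment, or pretreatment | Same |
| Day 1, after the first drop | New treatment | Same |

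The rules differ only in the first two rows.

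**2. Length of the assignment window.** Inputs: 2 dosing days per period, a washout of 7 to 21 days, screening from day -18 to day -1 (Protocol 3). The stated study duration confirms the cycle:

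- shortest: 1 + 5 × 2 + 4 × 7 = 39 days
- longest: 18 + 5 × 2 + 4 × 21 = 112 days

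Both match the protocol. A period with its washout therefore lasts 2 + 7 = 9 to 2 + 21 = 23 days. For the last period, with last dose + 30 days, the window is 2 + 30 = 32 days. I take the 30-day limit to apply to the last period only. Table 5-23 does not say so, and since 30 days exceeds the washout, that wording needs clarifying separately.

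**3. Exposed interval.** Midnight to a drop between 7 and 9 AM is 7 to 9 hours, or 7/24 = 29% to 9/24 = 38% of calendar day 1.

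**4. Share of the window**, assuming onset is uniform over time (the documents do not state this): share = (hours / 24) / window days.

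| Dosing time | 9 days | 16 days | 23 days | 32 days (last period) |
|---|---|---|---|---|
| 7 AM | 3.2% | 1.8% | 1.3% | 0.9% |
| 8 AM | 3.7% | 2.1% | 1.4% | 1.0% |
| 9 AM | 4.2% | 2.3% | 1.6% | 1.2% |

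**5. Mornings at risk.** With full retention, 160 patients × 5 periods = 800 first-day mornings: 160 in period 1 and 640 in periods 2 to 5. These are patient-mornings, not events, and the 12.5% dropout that the protocol anticipates would reduce them.

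**6. Imputed dates.** Under SAP Table 6-5 and 6.4.1, a fully missing AE start date is set to the treatment start date unless a complete end date is earlier. Such an event lands on day 1 with no known relation to the drop, so any split at the drop needs a rule for unknown timing.

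**The case against.** **A reader might infer that AEs are recorded without onset relative to the dose.** The documents do not show that. The line in Protocol 10.4.1 is part of a list of medical-record contents, and the AE form is not shown. Onset time is neither required nor excluded by the visible text. But if the form does hold a time, Table 5-23 as written does not use it.

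**A reader might infer that every event present before the first drop is charged to the new treatment.** It is not. The AE query looks back to the last visit, so in periods 2 to 5 many answers will carry washout dates and be assigned as intended. Only same-day onset or worsening is affected.

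**A reader might infer that signs first found at pre-dose examinations are all misassigned, making the true share higher.** No visible text says how such signs are dated, and the visit schedule is not visible. A pre-dose ocular examination is documented for period 1 only (Protocol 8.3).

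**The harm may be small in any case.** After 7 to 21 days of washout, a new complaint is probably background, and assigning it to the previous treatment is not clearly more accurate. Sequence is randomized and each sequence is used eight times per group, so background events should spread roughly evenly over treatments. Causality is judged for each AE, and treatment-related events are tabulated separately.

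These arguments stand as limits on the size: no direction of bias for the second hypothesis has been shown. They do not make the rule right. Randomized order does not help in period 1, where an event before any exposure is still labelled treatment-emergent, and the all-causality tables follow the date rule whatever the causality judgement.

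**Conclusion.** The narrow point holds. Table 5-23 and the Protocol Summary classify an AE that starts or worsens on the first day of a period, before the first drop, differently, and SAP 5.2.2 does not declare the difference. The SAP charges that event to a treatment not yet given.

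The effect is small: a few percent of a period's assignment window at most. The percentages rest on uniform onset, on drops given between 7 and 9 AM, and on reading the window as starting afresh each period. How many events would move cannot be determined. None would move if no AE starts or worsens in that interval. The documents do not support a claim that the safety comparison is materially biased. This is a low-cost correction worth making, not a threat to the trial's conclusions.

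**What to change.** **In SAP Table 5-23**, for events that start or worsen on the first dosing day of a period, count under that period's treatment only those that began or worsened after the first drop. Assign earlier ones to the preceding period's treatment, or to pretreatment in period 1. Apply the same split to the on-therapy definition, so that both agree with the protocol.

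**For the data**, use AE onset time if the AE form already captures it. If it does not, add one item for dosing days recording whether the event began or worsened before or after that day's first drop. The rule needs the answer only on the first day of each period.

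**For unknown timing**, including imputed start dates, keep the present date rule and flag the event, so that a reader can see how many assignments rest on it.

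The cost is one SAP amendment sentence and, at most, one form item. Sites must ask one more question, and a few events will stay unresolved.
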